7.1.5.2 Blinding/Unblinding

This is an open label trial; there is no blinding for this trial.

7.1.5.3 Calibration of Critical Equipment

The investigator or qualified designee has the responsibility to ensure that any critical device or instrument used for a clinical evaluation/test during a clinical trial that provides important information about inclusion/exclusion criteria and/or safety or efficacy parameters shall be suitably calibrated and maintained to ensure that the data obtained is reliable and/or reproducible. Documentation of equipment calibration must be retained as source documentation at the trial site.

Critical Equipment for this trial includes:

- Laboratory equipment – as required for inclusion labs and trial assessments
- Imaging equipment – as required for study objectives

See protocol-specified guidance in the Trial Administrative Binder, Procedures Manual, and Site Imaging Manual.

7.1.6 Visit Requirements

Visit requirements are outlined in Section 6.0 - Trial Flow Chart. Specific procedure-related details are provided above in Section 7.1 - Trial Procedures.

7.1.6.1 Screening

Approximately 28 days prior to treatment allocation, potential subjects will be evaluated to determine that they fulfill the entry requirements as set forth in Section 5.1. Screening procedures may be repeated.

Subjects may not be rescreened in this study.

Screening procedures are to be completed within 28 days prior to the first dose of trial treatment except for the following:

- Laboratory tests and ECOG PS are to be performed within 10 days prior to the first dose of trial treatment.
- For women of reproductive potential, a pregnancy test will be performed within 72 hours prior to the first dose of trial treatment. A urine test may be considered if serum test is not appropriate.

7.1.6.2 Treatment Period

Visit requirements are outlined in the Trial Flow Chart (Section 6.0). Specific procedure-related details are provided above in the Trial Procedures.

Subjects who stop pembrolizumab with SD or better may be eligible for up to 17 additional trial treatments (approximately 1 year) if they progress after stopping study treatments. Retreatment with pembrolizumab is termed the Second Course Phase and is only available if the trial remains open and the subject meets the following conditions:

- **Either**
 - Stopped initial treatment with pembrolizumab after attaining an investigator-determined confirmed CR according to RECIST 1.1
 - Was treated with at least 8 trial treatments (approximately 6 months) with pembrolizumab before discontinuing therapy
 - Received at least 2 treatments with pembrolizumab beyond the date when the initial CR was declared

OR

- Had SD, PR or CR and stopped pembrolizumab after 35 trial treatments (approximately 2 years) for reasons other than disease progression or intolerance
- **AND**
 - Experienced an investigator-determined confirmed radiographic disease progression after stopping their initial treatment with pembrolizumab
 - Did not receive any anti-cancer treatment since the last dose of pembrolizumab
 - Has a performance status of 0 or 1 on the ECOG Performance Scale
 - Demonstrates adequate organ function as detailed in Section 5.1.2

- Female subject of childbearing potential should have a negative serum or urine pregnancy test within 72 hours prior to receiving retreatment with study medication.
- Female subjects of childbearing potential (Section 5.7.2) must be willing to use an adequate method of contraception as outlined in Section 5.7.2 – Contraception, for the course of the study through 120 days after the last dose of study medication.
 - *Note: Abstinence is acceptable if this is the usual lifestyle and preferred contraception for the subject.*
- Male subjects of childbearing potential (Section 5.7.2) must agree to use an adequate method of contraception as outlined in Section 5.7.2 – Contraception and not to donate sperm starting with the first dose of study therapy through 120 days after the last dose of study therapy.
 - *Note: Abstinence is acceptable if this is the usual lifestyle and preferred contraception for the subject.*
- Does not have a history or current evidence of any condition, therapy, or laboratory abnormality that might interfere with the subject's participation for the full duration of the trial or is not in the best interest of the subject to participate, in the opinion of the treating investigator.

Subjects who enter the Second Course Phase will be retreated at the same dose frequency as when they last received pembrolizumab. Pembrolizumab will be administered for up to an additional 17 trial treatments (approximately 1 year).

Visit requirements for the second course phase are outlined in the Second Course Phase Trial Flow Chart (Section 6.2).

7.1.6.3 Post-Treatment Visits

7.1.6.3.1 Safety Follow-up Visits

The mandatory Safety Follow-up Visit should be conducted approximately 30 days after the last dose of trial treatment or before the initiation of a new anti-cancer treatment, whichever comes first.

All AEs that occur prior to the Safety Follow-Up Visit should be recorded. Subjects with an AE of Grade > 1 will be followed until the resolution of the AE to Grade 0-1 or until the beginning of a new anti-cancer therapy, whichever occurs first. SAEs that occur within 90 days of the end of treatment or before initiation of a new anti-cancer treatment should also be followed and recorded.

Subjects who are eligible for retreatment with pembrolizumab may have up to 2 safety follow-up visits, one after the Initial Treatment Period and one after the Second Course Treatment Phase.

7.1.6.3.2 Follow-up visits

Subjects who discontinue trial treatment for reasons other than disease progression will move into the Follow-up Phase and should be assessed Q9W by radiologic imaging to monitor disease status. The Sponsor may request survival status to be assessed at additional time points during the course of the study (not to exceed approximately 12 weeks). Every effort should be made to collect information regarding disease status until the start of a new anti-cancer therapy, disease progression, death, or the end of the study.

Information regarding post-study anti-cancer treatment will be collected if new treatment is initiated.

Subjects who are eligible to receive retreatment with pembrolizumab according to the criteria in Section 7.1.6.2 will move from the Follow-up Phase to the Second Course Phase when they experience disease progression.

7.1.6.3.3 Survival Follow-up

Subjects, who experience disease progression (by site assessment) or start a new anti-cancer therapy, will move into the Survival Follow-Up Phase. Subjects should be contacted by telephone approximately every 12 weeks to assess for survival status until death, withdrawal of consent, or the end of the study, whichever occurs first.

7.1.6.3.3.1 Survival Status

To ensure current and complete survival data is available at the time of database locks, updated survival status may be requested during the course of the study by the Sponsor. For example, updated survival status may be requested prior to but not limited to an external Data Monitoring Committee (eDMC) review, interim and/or final analysis. Upon Sponsor notification, all participants who do not/will not have a scheduled study visit or study contact during the Sponsor defined time period will be contacted for their survival status (excluding participants that have a previously recorded death event in the collection tool).

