5.8.2 Discontinuation of Study Therapy After Complete Response

Discontinuation of treatment may be considered for subjects who have attained a centrally confirmed CR, and who have received at least 8 cycles (approx. 6 months) of pembrolizumab, and who received at least 2 cycles of pembrolizumab beyond the date when initial CR was declared. Subjects who discontinue pembrolizumab therapy due to CR and

then experience radiographic disease progression may be eligible for up to 17 additional cycles (approx. 1 year) of pembrolizumab in the Second Course Phase, at the discretion of the investigator if:

- No cancer treatment was administered since the last dose of pembrolizumab
- The subject meets the parameters listed in the Inclusion/Exclusion criteria
- The trial is ongoing

Subjects will resume pembrolizumab therapy at the same dose level and on the same schedule as those at the time of initial discontinuation. Additional details are provided in Section 7.1.6.2. Response or progression in this Second Course Phase will not count towards the primary endpoint in this trial.

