7.1.4.1.3 End of Treatment and Follow-up Tumor Imaging

In subjects who discontinue trial treatment, tumor imaging should be performed at the time of treatment discontinuation (\pm 4-week window). If a previous scan was obtained within 4 weeks prior to the date of discontinuation, then a scan at treatment discontinuation isn't mandatory. In subjects who discontinue trial treatment due to documented disease progression, this is the final required tumor imaging.

In subjects who discontinue trial treatment without documented disease progression, every effort should be made to continue monitoring their disease status by tumor imaging using the same imaging schedule used while on treatment (every 9 weeks) to monitor disease status until (1) the start of new anti-cancer treatment, (2) disease progression, (3) death, or (4) the end of the study, whichever occurs first.

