7.1.4.1.5 RECIST 1.1 Assessment of Disease

RECIST 1.1 will be applied by the central imaging vendor as the primary measure for assessment of tumor response, date of disease progression, and as a basis for all protocol guidelines related to disease status (eg, discontinuation of study therapy).

7.1.4.1.6 irRECIST Assessment of Disease

irRECIST is RECIST 1.1 adapted as described below to account for the unique tumor response seen with immunotherapeutic drugs. irRECIST will be used by site investigator/local radiology review to assess tumor response and progression, and make treatment decisions. This data will be collected in the clinical database. Treatment efficacy based on irRECIST as assessed by central imaging vendor review will be evaluated retrospectively.

When feasible, subjects should not be discontinued until progression is confirmed by the local site investigator/radiology assessment. This allowance to continue treatment despite initial radiologic progressive disease (PD) takes into account the observation that some subjects can have a transient tumor flare in the first few months after the start of immunotherapy, and then experience subsequent disease response. Subjects that are deemed clinically unstable are not required to have repeat tumor imaging for confirmation of PD. Tumor flare includes any of the following scenarios:

- Worsening of existing target lesion(s)
- Worsening of existing non-target lesion(s)
- Development of new lesion(s)

In subjects who have shown initial evidence of radiological PD by RECIST 1.1 as determined by the site, it is at the discretion of the PI whether to continue a subject on study treatment until repeat imaging is obtained (using irRECIST for subject management, see [Table 6](#) and [Figure 2](#)). This clinical judgment decision by the site investigator should be based on the subject's overall clinical condition, including performance status, clinical symptoms, and laboratory data. Subjects may receive study treatment and tumor assessment should be repeated ≥ 4 weeks later in order to confirm PD by irRECIST per site assessment. Clinical stability is defined as the following:

- 1) Absence of symptoms and signs indicating clinically significant progression of disease, including worsening of laboratory values
- 2) No decline in ECOG performance status
- 3) Absence of rapid progression of disease

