8.4.1.2 Secondary Efficacy Endpoints

- **Duration of Response (DOR) - RECIST 1.1 assessed by central imaging vendor**

For subjects who demonstrated CR or PR, response duration is defined as the time from the date of first response (CR or PR) until the date of disease progression or death.

- **Progression-free Survival (PFS) - RECIST 1.1 assessed by central imaging vendor**

PFS is defined as the time from first day of study treatment to the first documented disease progression or death due to any cause, whichever occurs first.

- **Overall survival (OS)**

OS is defined as the time from first day of study treatment to death due to any cause. Subjects without documented death at the time of the final analysis will be censored at the date of the last follow-up.

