3.4.1.2 Secondary Efficacy Endpoints

- Disease Control Rate (DCR) - RECIST 1.1 assessed by central imaging vendor**

Disease control rate (DCR) is defined as the percentage of subjects who have achieved confirmed CR or PR or have demonstrated SD prior to any evidence of progression.

- Duration of Response (DOR) - RECIST 1.1 assessed by central imaging vendor**

For subjects who demonstrate CR or PR, duration of response is defined as the time from first documented evidence of CR or PR until disease progression or death due to any cause, whichever occurs first.

- Progression-free Survival (PFS) - RECIST 1.1 assessed by central imaging vendor**

PFS is defined as the time from first day of study treatment to the first documented disease progression or death due to any cause, whichever occurs first.

- **Overall survival (OS)**

OS is defined as the time from first day of study treatment to death due to any cause. Subjects without documented death at the time of the final analysis will be censored at the date of the last follow-up.

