Table 2 Censoring rules for PFS analysis

Situation	Primary Analysis
No PD and no death; new anticancer treatment is not initiated	Censored at last disease assessment
No PD and no death; new anticancer treatment is initiated	Censored at last disease assessment before new anticancer treatment

Table 3 Analysis Strategy for Efficacy Variables

Endpoint/Variable [‡] (Description, Time Point)	Statistical Method	Analysis Population	Missing Data Approach
Primary Endpoint and Hypothesis			
ORR • RECIST 1.1, Central imaging vendor assessment	Exact method based on binomial distribution	ASaT • All subjects • Subjects whose tumors classified as “GEP intermediate or high” (GEP \geq -1.540) • Subjects whose tumors classified as “GEP high” (GEP \geq -0.945)	Subjects with missing data are considered non-responders

Endpoint/Variable [‡] (Description, Time Point)	Statistical Method	Analysis Population	Missing Approach	Data
Secondary Endpoints				
DCR • RECIST 1.1, Central imaging vendor assessment	Exact method based on binomial distribution	ASaT	Subjects with missing data are considered as disease not under control	
DOR • RECIST 1.1, Central imaging vendor assessment	Summary statistics using Kaplan-Meier method	All responders	Non-responders are excluded from analysis	
PFS • RECIST 1.1, Central imaging vendor assessment	Summary statistics using Kaplan-Meier method	ASaT	Censoring rules follow Table 2 .	
OS	Summary statistics using Kaplan-Meier method	ASaT	Censored at last known alive date	
Exploratory Endpoints				
ORR • irRECIST, Central imaging vendor assessment	Exact method based on binomial distribution	ASaT • All subjects • Subjects whose tumors classified as “GEP intermediate or high” (GEP \geq - 1.540) • Subjects whose tumors classified as “GEP high” (GEP \geq - 0.945)	Subjects with missing data are considered non-responders	

Endpoint/Variable [‡] (Description, Time Point)	Statistical Method	Analysis Population	Missing Data Approach
PFS • irRECIST, Central imaging vendor	Summary statistics using Kaplan-Meier method	ASaT	Censoring rules per irRECIST also follow Table 2 . If there is no confirmation scan available after the initial PD scan, then it is considered as a PFS event at the initial PD scan time point.

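### PFS and DOR need a central RECIST 1.1 progression, but required scanning ends on the site's progression call, so some central progressions are missed and both curves tend to run slightly long

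*Combined protocol and SAP*

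**What the plan says.** **Who defines the event.** Protocol 8.4.1.2 and sSAP 3.4.1.2 list "Progression-free Survival (PFS) - RECIST 1.1 assessed by central imaging vendor", and the sSAP lists "Duration of Response (DOR) - RECIST 1.1 assessed by central imaging vendor". In the sSAP, "PFS is defined as the time from first day of study treatment to the first documented disease progression or death due to any cause".

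**Who ends the scanning.** Protocol 7.1.6.3.3: "Subjects, who experience disease progression (by site assessment) or start a new anti-cancer therapy, will move into the Survival Follow-Up Phase". From there, contact is by telephone. Protocol 7.1.4.1.3: "In subjects who discontinue trial treatment due to documented disease progression, this is the final required tumor imaging". Table 6 asks for no more imaging once the site has confirmed PD. Under 7.1.4.1.6 a clinically unstable subject stops treatment at the first site PD and needs no repeat scan. A stable subject is expected to have a repeat scan at least 4 weeks later (7.1.4.1.2). Footnote a of the flow chart in 6.1 makes confirmed site PD the trigger for survival follow-up.

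**What the sSAP does next.** Both rows of sSAP Table 2 (PFS censoring) require that there is no PD and no death; the first reads "No PD and no death; new anticancer treatment is not initiated". There is no missed-assessment rule. sSAP Table 1 (DOR) censors at the last adequate scan once two or more consecutive assessments are missed, and counts a death after at most one missed assessment as an event.

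**Site data.** Of the site's assessments, 7.1.4.1.6 says: "This data will be collected in the clinical database". No planned PFS or DOR analysis uses them.

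**Retreatment.** Protocol 5.8.2: "Response or progression in this Second Course Phase will not count towards the primary endpoint in this trial". It does not mention PFS or DOR.

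**The concern.** One assessor decides when observation ends and another decides whether an event occurred. Suppose the site calls PD and the central reader, looking at the same scans, does not. The subject then leaves imaging because a clinician judged the disease to have progressed, so the loss of follow-up is related to the outcome. The effect is one-sided. All scans go to the vendor, so a central PD earlier than the site's is captured, while a later one is usually lost.

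The two endpoints are affected differently. For PFS the event moves to the date of death, however late, or the subject is censored at the last scan if alive at data cut-off. For DOR a late death is not an event, and the subject is censored at the last adequate scan. Table 1 does not say whether scans that are no longer required count as missed.

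The trial has a single arm, so these curves are read at face value. The exploratory irRECIST analyses do not help, because they use the same central reader and the same truncated scans.

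**Working it through.** **Plan figures.** The documents state no expected median, event count or precision for PFS or DOR, so there is nothing to reproduce for them. The only design figures are the exact ORR intervals. All 11 (protocol Tables 9-11, repeated as sSAP Tables 4-6) reproduce to one decimal, for example 17/100 giving 10.2% to 25.8%. This point does not touch them.

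**Method.** Direction and size come from Kaplan-Meier simulation, 200,000 subjects per scenario.

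- From the documents: scans every 9 weeks; the rules of sSAP Tables 1 and 2; a 40-week median DOR in the earlier esophageal cohort (protocol 4.2.1), used only to scale the DOR runs.
- Assumed: exponential times; a share d of site PDs that the central reader does not call at that scan; a later central call delayed by a geometric number of scans.
- Comparator: imaging continued until central PD, which is the endpoint as defined.
- Plan: for subjects lost to imaging, PFS is the death date, or censored at the site PD scan if alive at cut-off. DOR is the same, except that a death more than 2 × 9 = 18 weeks after that scan is censored at the scan.
- Excess = S(t) under the plan minus S(t) with continued imaging.

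**Set A.** Median time to PD 13 weeks (PFS) or median response 40 weeks (DOR), median post-progression survival 15 weeks, follow-up 26-78 weeks, no confirmation scan.

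| d | 26-week PFS: plan vs continued | Excess | 52-week DOR: plan vs continued | Excess |
|---|---|---|---|---|
| 10% | 38% vs 37% | 1 | 46% vs 45% | 1 |
| 20% | 41% vs 39% | 2 | 48% vs 46% | 2 |
| 30% | 43% vs 41% | 2 | 49% vs 46% | 3 |

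Median PFS is 18 weeks throughout. If half of the discordant subjects have a confirmation scan, 26-week PFS under the plan is 37%, 39% and 41%, and the excess is gone.

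**Set B.** A wider grid: d from 5% to 30%; median time to PD 8 or 16 weeks; median response 26 or 40 weeks; median post-progression survival 14-26 weeks; confirmation scan in 0% or 50% of discordant cases. The late landmark rate was higher under the plan in every scenario: by 0.4 to 7.3 points for 39-week PFS and 0.2 to 3.7 points for 52-week DOR.

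- Largest PFS excess (8 weeks to PD, 26 weeks after, d = 30%, no confirmation): 14.7 − 7.4 = 7.3 points. With half confirmed: 11.9 − 7.5 = 4.4 points.
- Largest DOR excess (median 26 weeks, d = 30%, no confirmation): 35.8 − 32.1 = 3.7 points. With half confirmed: 33.7 − 32.0 = 1.7 points.
- Medians mostly stay put because they sit on the 9-week grid. Exceptions include PFS 21.9 to 25.5 weeks (16 weeks to PD, d = 20%) and DOR 45 to 54 weeks (median 40, d = 30%). In a few runs with confirmation scans the median was shorter, because the extra scan dated PD earlier.

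**The case against.** The confirmation pathway is the best answer. A reader might infer that a central PD can never be recorded once the site has called PD. The documents do not support that. Stable subjects are expected to have a repeat scan, unconfirmed PD returns to regular imaging, and imaging continues under the Sponsor-agreed exception. Those scans go to the vendor, so the central reader often gets a second look. What stands is the gap for clinically unstable subjects, and for PD still not called centrally after confirmation.

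A reader might also infer a much larger bias, in two ways.

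- Treating every site PD as the truth compares 38%, 41% and 43% for 26-week PFS with about 36%, a gap of 2, 5 and 7 points. Part of that gap is only a change of assessor. The defined endpoint is central PD.
- Censoring every discordant responder at the last scan lifts 52-week DOR from about 46% to 50%, 54% and 59%, or 4, 8 and 13 points. Table 1 does not do this, because it counts an early death as an event.

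It is also fair to say that protocol 7.1.4.1.5 names central RECIST 1.1 as the basis for disease-status rules, including stopping study therapy. That does not close the gap. It conflicts with the site-based rules in 2.1, 7.1.4.1.2, 7.1.4.1.6 and 7.1.6.3.3, and the passages must be reconciled.

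Finally, these endpoints are secondary and descriptive, with no test or threshold attached. That limits the weight of the point without removing it.

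**Conclusion.** The mismatch is in the text and tends to lengthen both curves, mainly in the tail. At an assumed 10-30% discordance, the excess over imaging continued to central PD is about 1-2 points for 26-week PFS and 1-3 points for 52-week DOR. Over 5-30% and a wider set of assumptions it is 0.4-7.3 points for 39-week PFS and 0.2-3.7 points for 52-week DOR. Confirmation scans shrink it. In Set A they remove the 26-week PFS excess; in Set B they reduce the later ones without removing them.

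The discordance rate, the central delay and the survival times are assumptions, since the documents give no discordance rate. That is a reason to report the count.

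The Second Course is a smaller, unquantified part of the same gap. Entry needs investigator-determined confirmed PD (7.1.6.2) and is open only after CR or 35 treatments. Tables 1 and 2 do not say whether retreatment is new anti-cancer therapy. A subject without central PD could therefore go on accruing PFS and DOR during retreatment.

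**What to change.** In sSAP 3.6.1, keep the central analysis as the main one and make these changes:

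1. Add one supportive PFS and one supportive DOR analysis in which the event is the earliest of central PD, site PD or death. Date site PD at the first site RECIST 1.1 PD scan that was later confirmed, or that was not followed by a repeat scan.
2. Report the number of subjects with site PD but no central PD.
3. State that Second Course time does not extend PFS or DOR. Censor the central analysis at the last scan before the first Second Course dose. In the supportive analysis, count the investigator PD that qualified the subject for retreatment as the event. Censoring alone would repeat the problem, because entry itself requires a judgement of progression.
4. State whether scans not required after site PD count as missed in Table 1.

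In the protocol, reconcile 7.1.4.1.5 with 7.1.4.1.2, 7.1.4.1.6, Table 6 and 7.1.6.3.3. Which rule governs treatment is for the sponsor to settle.

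The cost is sSAP wording and one extra table and curve per endpoint, with no new scans or central reads. Site assessments are already collected, though the sponsor should check that the date of the first site PD scan can be derived. The drawback is a second, slightly less favourable figure that mixes assessors.
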